- A. Experimental group: low impact laparoscopy (low pressure (8 mmHg) and deep NMB (PTC 1-2))

B. Control group: standard laparoscopy (standard pressure (14 mmHg) and moderate NMB (TOF 1-2))

At the start of surgery, after intra-abdominal insufflation, ICG injection will take place to quantify *parietal peritoneum* perfusion, and a parietal peritoneal biopsy will be taken. At the end of surgery, a second parietal peritoneum biopsy will be taken.

Main study parameters/endpoints:

Primary endpoints

- Quality of recovery score (QoR-40) at postoperative day 1.
- IL-6 and IL-10 response upon whole blood LPS stimulation at postoperative day 7.
- Perfusion index of the parietal peritoneum as calculated from the slope of ICG fluorescence intensity, and time to maximal intensity in seconds. (extracted from video registration).

Secondary endpoints

- QoR-40 score (day 1 and day 10-12), SF-36 score (1 day before, 10-12 days and 3 months after surgery), McGill pain questionnaire (3 months after surgery).
- Pain scores, analgesia use, PONV, time to reach discharge criteria, length of hospital stay, surgical conditions and postoperative complications scored by Clavien Dindo classification (table 2 (1)).

Nature and extent of the burden and risks associated with participation:

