4.4 Sample size calculation

The main study includes 48 patients per study arm (low impact and standard laparoscopy). With this number of patients we will have sufficient power for the primary and secondary analyses:

- 1) Quality of recovery at POD 1 as reflected by the QoR-40 questionnaire. Although Myles et al. reported a minimal clinically relevant difference (MCID) of 6.3 for the QoR-40 questionnaire, consensus about the MCID is lacking. As 6.3 is a relatively small difference on a scale ranging from 40-200, we feel that a MCID of 10 points is more appropriate. A sample size of 48 patients per group is needed to provide 90% power to detect a 10 point difference in the QoR-40 at POD 1 (alpha 5%) with an estimated standard deviation of 15.
- 2) Innate immune function as reflected by the *ex vivo* release of IL-6 and IL-10 upon LPS stimulated leukocytes at POD 7. A sample size of 45 patients per group is needed to provide 90% power to detect a 3.000 pg/mL difference in IL-6 release (alpha 2.5%) with an estimated standard deviation of 4.000 pg/mL at POD 7. A sample size of 42 patients per group is needed to provide 90% power to detect a 50 pg/mL difference in IL-10 release (alpha 2.5%) with an estimated standard deviation of 65 pg/mL. As two cytokines are measured, a Bonferroni correction was used (alpha 2.5%).

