8 METHODS

8.1 Main study endpoints

- Quality of recovery score (QoR-40) at postoperative day 1.
- IL-6 response upon whole blood LPS stimulation at postoperative day 10-12
- Perfusion index of the parietal peritoneum as calculated from the slope of ICG fluorescence intensity, and time to maximal intensity in seconds. (extracted from video registration).

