8.2 Other study parameters

General

- Baseline parameters as age, gender, length, weight, body mass index, comorbidity, indication for and type of surgery.
- Intraoperative parameters routinely measured (at administration of ICG): blood pressure, temperature and level of NMB (train of four response).

Questionnaires

- Quality of recovery score (QoR-40) at 1 day before surgery and day 10-12 after surgery.
- SF-36 general health questionnaire (Dutch version) 1 day before surgery, day 10-12 and 3 months after surgery.
- McGill pain Questionnaire 3 months after surgery

Pain scores

- Pain at rest and movement (NRS 0-10) at 1, 8, 24, 72 hours after surgery
- Is pain acceptable (yes/no) at 1, 8, 24, 72 hours after surgery
- Referred shoulder pain (yes/no) at 1, 8, 24, 72 hours after surgery

PONV

- PONV (yes/no) at 1, 8, 24 and 72 hours after surgery

Medication use

- Cumulative opiate use
- Cumulative use of other analgesics and anti-emetics

Clinical parameters

- Time to reach discharge criteria*
- Length of hospital stay
- Surgical conditions: Leiden Surgical Rating Scale to quantify the quality of the surgical field during the pneumoperitoneum phase (after introduction of the Hasson trocar, after introduction of the third trocar and then every 15 minutes)
- Postoperative complications scored by Clavien Dindo classification (table 2 (1))

Immune function

- Peritoneal mesothelial hypoxia as reflected by peritoneal HIF1-alfa mRNA expression
- Histological peritoneal mesothelial cell injury.
- Plasma levels of DAMPs, cytokines and ex vivo immune function at baseline, 24 hours after surgery and 10-12 days after surgery.

*discharge criteria are: adequate pain control with oral medication, passage of flatus or defecation, intake of solid food tolerated, patient is mobilized and independent and patient accepts discharge. Discharge criteria will be evaluated daily. If the donor for social reasons wants to stay longer (e.g. long distance from partner of child who are still hospitalized) the 'virtual' discharge date is listed. A physician who is independent and blinded (ward physician) is responsible for the actual discharge date.

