10.1 Primary study parameter(s)

- Quality of recovery score (QoR-40) at postoperative day 1.
- For QOR-40 score, factorial ANCOVA will be used to compare groups and to adjust for co-variates *i.e.* age and gender. P-values <0.05 will be considered statistically significant.
- IL-6 response upon whole blood LPS stimulation at postoperative day 7.
- For mononuclear cell responsiveness, ANCOVA will be used to compare groups and to adjust for co-variates *i.e.* age and gender. As the primary endpoint includes changes in both IL-6 and IL-10 release, Bonferroni correction for multiple comparisons will be used. P-values < 0.025 will be considered statistically significant.
- Perfusion index in sigmoid as calculated from the slope of ICG fluorescence intensity, and time to maximal intensity in seconds. (extracted from video registration).
- Factorial ANCOVA will be used to compare groups and adjust for covariates *i.e.* age and gender. P-values <0.05 will be considered statistically significant.

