13.2 Synthesis

As explained in the rationale, the use of deep NMB enables safe use of low-pressure PNP. If visibility is compromised at low pressure, pressure will be increased to ensure no additional risks related to the surgery. A deep NMB is achieved by higher doses of rocuronium that are within normal therapeutical range used in clinical practice, and can safely be used. Depth of NMB will be monitored throughout the whole surgery. At the end of surgery, the effects of rocuronium are antagonized by sugammadex to ensure no extended effects. Randomized controlled trials have shown sugammadex can be safely administered. Regarding the biopsies, peritoneal tissue is directly visible and easily accessible during laparoscopic surgery in the pelvis. After biopsy, hemostasis will be established under direct vision and therefore no additional complications are to be expected. Previous studies have shown low-pressure PNP is associated with reduced postoperative pain scores, reduced opioid consumption and improved bowel function. The burden for participants is mainly related to the evaluation of the endpoints during the early postoperative phase. Assessment of the pain scores and the QOR-40 questionnaire will take approximately 10-15 minutes per time-point. Blood samples will be combined with routine laboratory assessment as much as possible, this is standard before- and 24 hours after surgery. Blood samples taken during surgery (while under anesthesia) and 10-12 days after surgery will be drawn by venapuncture if necessary.

Figure 6: Perioperative flowchart

[figure not shown]

Table 1: Leiden Surgical-Rating-Scale (L-SRS) (25)

Scale	Description	
1	Extremely poor conditions	The surgeon is unable to work because of coughing or the inability to obtain a visible laparoscopic field because of inadequate muscle relaxation.
2	Poor conditions	There is a visible laparoscopic field, but the surgeon is severely hampered by inadequate muscle relaxation with continuous muscle contractions, movements or both with the hazard of tissue damage.
3	Acceptable conditions	There is a wide visible laparoscopic field but muscle contractions, movements or both occur regularly causing some interference with the surgeon's work.
4	Good conditions	There is a wide laparoscopic field with sporadic muscle contractions, movements or both.
5	Optimal conditions	There is a wide visible laparoscopic working field without any movement or contractions.

Table 2: Clavien Dindo classification(1)

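### The primary LPS-stimulated cytokine endpoint is set at day 7 in the synopsis, 4.4 and 10.1 but at day 10-12 in 8.1; the visible schedule has no day 7 blood draw, and power is not shown for day 10-12.

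*Combined protocol and SAP*

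**What the plan says.** Three places put the endpoint at day 7. The synopsis lists as primary the "IL-6 and IL-10 response upon whole blood LPS stimulation at postoperative day 7". Section 4.4 bases its second power calculation on "release of IL-6 and IL-10 upon LPS stimulated leukocytes at POD 7" and gives the IL-6 variability "with an estimated standard deviation of 4.000 pg/mL at POD 7". Section 10.1 names the "IL-6 response upon whole blood LPS stimulation at postoperative day 7".

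Section 8.1, which lists the main study endpoints, instead gives the "IL-6 response upon whole blood LPS stimulation at postoperative day 10-12".

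The sampling text follows 8.1. Section 8.2 schedules "Plasma levels of DAMPs, cytokines and ex vivo immune function at baseline, 24 hours after surgery and 10-12 days after surgery". Section 13.2 says of routine blood work that "this is standard before- and 24 hours after surgery", and adds: "Blood samples taken during surgery (while under anesthesia) and 10-12 days after surgery will be drawn by venapuncture if necessary". In Table 3 the blood column is marked at day -1, 24 hours and days 10-12, and the table has no day 7 row.

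Two smaller differences go with this. Section 8.1 and the endpoint bullet in 10.1 name IL-6 alone, although the analysis bullet that follows in 10.1 covers IL-6 and IL-10 at 0.025 each. Section 8.3 introduces the blood samples under secondary immune endpoints, while 10.2 labels ex vivo immune function as the second primary endpoint.

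**The concern.** The analysis section specifies a primary test on a day for which the visible schedule collects no blood. Someone following 10.1 as written would have no documented sample to analyse.

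If the analysis moves to the day that is sampled, the power statement does not move with it. The difference and SD in 4.4 are stated for day 7, and the documents give neither for day 10-12. The ratio of difference to SD is what counts. Power holds if both fall in proportion, and drops if the difference shrinks or the SD grows alone.

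There is also a prespecification problem. If two days are still named when the allocation is revealed, a reader cannot tell which primary immune test was chosen in advance.

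**Working it through.** **Endpoint day and sampling, side by side**

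| Place | Day of primary cytokine endpoint | Blood draws listed |
|---|---|---|
| Synopsis | 7 | – |
| 4.4 | 7 | – |
| 10.1 | 7 | – |
| 8.1 | 10-12 | – |
| 8.2 | – | baseline, 24 h, day 10-12 |
| 13.2 | – | before, during and 24 h after surgery, day 10-12 |
| Table 3 | – | day -1, 24 h, day 10-12 |

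No list contains day 7.

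**Reproducing 4.4**

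Inputs from 4.4: IL-6 difference 3,000 and SD 4,000 pg/mL; IL-10 difference 50 and SD 65 pg/mL; alpha 2.5% (taken as two-sided); power 90%. With r = difference/SD, the normal approximation is n per arm = 2(z₀.₉₈₇₅ + z₀.₉₀)²/r² = 2(2.2414 + 1.2816)²/r² = 24.82/r².

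- IL-6: r = 3000/4000 = 0.750; n = 24.82/0.5625 = 44.13, rounded up to 45. The plan states 45.
- IL-10: r = 50/65 = 0.769; n = 24.82/0.5917 = 41.95, rounded up to 42. The plan states 42.

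Both figures reproduce, so the arithmetic is sound for day 7.

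**Power at the planned 48 per arm if the test is done at day 10-12**

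This uses a two-sample t-test with 94 degrees of freedom, noncentrality r × √(48/2) = 4.899 r and two-sided alpha 2.5%. For IL-6 with inputs unchanged, the noncentrality is 4.899 × 0.750 = 3.674 and power is 0.917. The day 10-12 scenarios are assumptions, because the documents give no values for that day.

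| Assumed at day 10-12 | IL-6 power | IL-10 power |
|---|---|---|
| Difference and SD both unchanged | 91.7% | 93.0% |
| Difference × 0.9 and SD × 0.9 | 91.7% | 93.0% |
| Difference × 0.9, SD unchanged | 84.6% | 86.5% |
| Difference × 0.75, SD unchanged | 68.3% | 70.8% |
| Difference unchanged, SD × 1.1 | 85.4% | 87.2% |
| Difference unchanged, SD × 1.25 | 74.5% | 76.8% |

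**Margin**

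- 90% power needs r of at least 0.729. That is 0.729/0.750 = 97% of plan for IL-6 and 0.729/0.769 = 95% for IL-10.
- With the difference unchanged, the SD could rise only to 4,116 pg/mL (IL-6, +2.9%) or 68.6 pg/mL (IL-10, +5.5%) before power falls below 90%.
- 80% power needs r of at least 0.638, about 85% and 83% of plan.

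Any gain in precision from the planned ANCOVA is unknown and not counted. The figures assume 48 analysable patients per arm.

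**The case against.** The strongest reply is that the missing day 7 draw may reflect an incomplete schedule. Section 8.2 covers other parameters and can leave out primary time points; its QoR-40 line omits postoperative day 1. Table 3 departs from the text elsewhere. It has no mark for the draw during surgery named in 13.2, and it shows a 48-hour row where 8.2 schedules pain and nausea at 72 hours. Figure 6 is not shown. A day 7 draw therefore cannot be strictly excluded.

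That limit stands, but it does not remove the problem. Section 8.3 presents Table 3 as the overview of measurements for both primary and secondary endpoints, and its blood column agrees with 13.2. Even if Figure 6 showed a day 7 draw, 8.1 would still contradict 10.1.

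A second reply is that nothing in the documents suggests a smaller difference or larger SD at day 10-12, and that 48 per arm exceeds the stated 45 and 42. This is right as far as it goes. It supports saying that 90% power is not shown for day 10-12, and does not support saying that it is lost.

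The conflict over primary or secondary status is weak. The wording in 8.3 may refer to the other immune measures taken from the same blood, and 10.2 labels QoR-40 in the same way.

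**Conclusion.** The concern holds. The current text gives two different days for one of the primary endpoints, and the day used for the sample size and analysis has no blood draw in any visible list. The sample size arithmetic is correct for day 7. For day 10-12 the 90% claim is unsupported: power would be 92% and 93% if the day 7 inputs apply unchanged, and it falls below 90% once the difference/SD ratio is more than about 3% (IL-6) or 5% (IL-10) under plan. How far the ratio would actually change is unknown.

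This must be corrected before unblinding. The contradiction itself is certain from the text; the absence of a day 7 draw is limited to what is visible. The cytokine naming and the status labels are wording matters that should be tidied in the same edit.

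**What to change.** Before unblinding, confirm which samples exist and set one day throughout.

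- **Day 10-12 (fits the visible sampling lists and 8.1).** Replace day 7 with day 10-12 in the synopsis, 4.4 and 10.1. Restate the difference, SD and power in 4.4 as assumptions for day 10-12 and give the reason for each value; relabelling the day 7 inputs would not close the gap. Cost: no extra draws or patients, but the restated power may be less favourable.
- **Day 7.** Change the endpoint in 8.1 to day 7 and add a day 7 draw to 8.2, 13.2 and Table 3. This works only if sampling can still change for all patients. Cost, unless a draw already exists outside the visible text: a new time point and one more draw per patient. Anyone already past day 7 without a sample would have no primary immune value.

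On either route, name both IL-6 and IL-10 in 8.1 and in the endpoint bullet of 10.1, each tested at 0.025, and give ex vivo immune function one status in 8.3 and 10.2.

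Both routes need a protocol amendment. Section 12.3 provides for notifying the METC but exempts non-substantial amendments; a change to a primary endpoint's time point should be treated as substantial and notified.

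A separate wording correction can go in with it: the perfusion endpoint in 10.1 refers to the sigmoid, where 8.1 has the parietal peritoneum.

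### Holm's step-down in place of single-step Bonferroni for IL-6 and IL-10 would raise power at the same 5% familywise error for the pair

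*Combined protocol and SAP*

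**What the plan says.** Section 10.1 justifies the correction by the content of the endpoint ("As the primary endpoint includes changes in both IL-6 and IL-10 release") and gives the decision rule as "Bonferroni correction for multiple comparisons will be used. P-values < 0.025 will be considered statistically significant". Each cytokine is therefore held to 0.025 whatever the other one shows.

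Section 4.4 plans on that threshold. For IL-6 it assumes a "3.000 pg/mL difference in IL-6 release (alpha 2.5%) with an estimated standard deviation of 4.000 pg/mL at POD 7" and concludes "A sample size of 45 patients per group is needed to provide 90% power". For IL-10 it assumes a "50 pg/mL difference in IL-10 release (alpha 2.5%) with an estimated standard deviation of 65 pg/mL" and concludes "A sample size of 42 patients per group is needed to provide 90% power". The trial itself is larger, because QoR-40 sets the size: "The main study includes 48 patients per study arm (low impact and standard laparoscopy".

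The documents contain no step-down, gatekeeping or other sequential rule, give no reason for preferring the single-step version, and do not say whether success on the immune endpoint needs one cytokine or both.

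**The concern.** Once one of two hypotheses has been rejected at 0.025, the other can be tested at 0.05 and the probability of any false rejection in the pair is still at most 5%, whatever the correlation. That is Holm's procedure. Under the rule in 10.1, p = 0.001 for IL-6 with p = 0.04 for IL-10 yields one claim. Under Holm it yields two, within the same 5% limit.

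What is at stake is the power for each cytokine and, more so, for both together. The second matters for interpretation, because section 1 describes immune suppression through both markers: reduced IL-6 and increased IL-10 production after ex vivo LPS stimulation.

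**Working it through.** **Inputs (section 4.4).** IL-6: d = 3000/4000 = 0.75. IL-10: d = 50/65 = 0.769. Per-test alpha 0.025, power 90%, 1:1 allocation, 48 per arm. Alpha is taken as two-sided. The documents do not say so, but only the two-sided formula returns their figures (one-sided gives 38 and 36).

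**Reproducing the plan.** n per group = 2(z₁₋α/₂ + z₀.₉₀)²/d².
- IL-6: 2(2.2414 + 1.2816)²/0.75² = 44.1, so 45.
- IL-10: 2(2.2414 + 1.2816)²/0.769² = 41.9, so 42.
- QoR-40 (10/15, alpha 0.05): 2(1.9600 + 1.2816)²/0.667² = 47.3, so 48.

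All three match.

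**Single-test power at 48 per arm** (two-sample t-test, 94 df, noncentrality d√24).

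| | alpha 0.025 | alpha 0.05 |
|---|---|---|
| IL-6 | 0.9167 | 0.9532 |
| IL-10 | 0.9301 | 0.9616 |

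**Bonferroni against Holm with uncorrelated cytokines.**
- Both, Bonferroni: 0.9167 × 0.9301 = 0.853.
- Both, Holm (both below 0.05 and at least one below 0.025): 0.9532 × 0.9616 − (0.9532 − 0.9167)(0.9616 − 0.9301) = 0.9166 − 0.0011 = 0.915.
- IL-6, Holm: 0.9167 + (0.9532 − 0.9167) × 0.9301 = 0.951.
- IL-10, Holm: 0.9301 + (0.9616 − 0.9301) × 0.9167 = 0.959.
- At least one, either method: 1 − (1 − 0.9167)(1 − 0.9301) = 0.994. It is identical because Holm's first step is the Bonferroni test.

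**Other correlations.** The IL-6/IL-10 correlation is not in the documents, so it is assumed over a range. Simulated t-tests, 400,000 trials per setting, 48 per arm, Bonferroni to Holm:

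| Correlation | IL-6 | IL-10 | Both | At least one |
|---|---|---|---|---|
| -0.5 | 91.7% to 95.3% | 93.0% to 96.1% | 84.7% to 91.5% | >99.9%, unchanged |
| 0 | 91.7% to 95.1% | 93.0% to 95.9% | 85.3% to 91.5% | 99.4%, unchanged |
| 0.5 | 91.7% to 94.6% | 93.1% to 95.4% | 87.0% to 92.2% | 97.9%, unchanged |

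A normal approximation taken out to a correlation of 0.8 shrinks the gain for both to about 4 points (89.7% to 93.5%).

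**Error control.** With both nulls true, the familywise error was 4.6% to 5.0% and the same under the two methods. With IL-10 null and IL-6 at its planned effect, the chance of a false IL-10 claim is 2.5% under Bonferroni. Under Holm with zero correlation it is 0.025 + 0.025 × 0.9167 = 0.048, and 4.6% to 4.8% across the simulated range. No simulated trial was rejected by Bonferroni but not by Holm.

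**The case against.** The plan's rule is prespecified, valid and the same in 4.4 and 10.1. At 48 per arm it already gives each cytokine more than the planned 90% power. Preferring a more efficient valid procedure to a simpler one can be called a matter of taste. All of that stands as a limit on how strongly the point can be put.

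A reader might go further and infer that Bonferroni costs power for no return. That is not so. It holds each cytokine's own false-positive risk at 2.5% even when the other is truly affected, where Holm lets it approach 5%. Its decisions also match simple 97.5% confidence intervals, whereas Holm's do not match any simple interval. Both are real but small costs of changing.

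A reader might also infer from section 1 that the trial must show both markers. The documents set no such success condition. If both were required, no correction would be needed: each could be tested at 0.05, with power 0.9532 × 0.9616 = 91.7% at zero correlation, much the same as Holm's 91.5%. If either one sufficed, Holm would not change the chance of success, only which individual claims could be made. Holm serves the plan as written, which corrects for two cytokines and so makes a separate claim on each.

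Finally, the family is not stated consistently. The synopsis and 4.4 name IL-6 and IL-10 at day 7, the endpoint bullet in 10.1 names IL-6 alone at day 7, and 8.1 names IL-6 alone at day 10-12. If IL-6 alone were primary, neither correction would apply. That needs settling separately. It does not alter the comparison while 10.1 corrects for two tests.

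**Conclusion.** The point holds as an inexpensive efficiency improvement. At the planned effects, Holm adds about 3 points of power per cytokine and about 5 to 7 points for showing both. It adds nothing for at least one, and the pair's familywise error stays within 5%.

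The error control and the dominance over Bonferroni hold under any correlation. The size of the gain rests on the effects and SDs in 4.4, approximately normal data, 48 evaluable patients per arm, unadjusted t-tests standing in for the planned ANCOVA, and an assumed correlation of -0.5 to 0.5. Gains would be larger if the true effects were smaller than planned, but the documents give no such scenario, so no figure for one is offered here.

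The 5% should not be read as covering the primary endpoints as a whole. QoR-40 and the perfusion index are each tested at 0.05 outside this correction, and changing the rule for the pair leaves that as it is.

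**What to change.** Before the unblinding described in section 10, replace the decision rule for the two cytokines in 10.1 with:

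> The smaller of the IL-6 and IL-10 p-values is compared with 0.025; if significant, the larger is compared with 0.05 (Holm).

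Align the Bonferroni sentence in 4.4. The figures of 45 and 42 per group stand, because Holm's first step is the 2.5% test they were built on. Add a sentence stating how confidence intervals for the two cytokines will be formed and that simple intervals need not agree with the Holm decisions. Say also that the 5% applies to the cytokine pair only.

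The cost is a few sentences in two sections. Patient numbers, procedures and data collection do not change. Dating the change before unblinding keeps it from looking data-driven.

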Rationale: Intra-abdominal pressure (IAP) needed to create sufficient workspace during laparoscopic surgery affects the surrounding organs with ischemia-reperfusion injury and a systemic immune response. This effect is related to postoperative recovery, pain scores, opioid consumption, bowel function recovery, morbidity and possibly mortality. In clinical practice standard pressures of 12-16mmHg are applied instead of the lowest possible IAP, but accumulating evidence shows lower pressure pneumoperitoneum (PNP) (6-8mmHg) to be non-compromising for sufficient workspace, when combined with deep neuromuscular blockade (NMB) in a vast majority of patients. Therefore, low impact laparoscopy, meaning low pressure PNP facilitated by deep NMB, could be a valuable addition to Enhanced Recovery After Surgery (ERAS) Protocols.

Increased IAP can cause peritoneal mesothelial injury either directly or by compression of small vessels including capillaries, leading to a variable degree of ischemia reperfusion injury. The compromised perfusion of the parietal peritoneum can be visualized and quantified by a fluorescent marker such as Indocyanine green (ICG), as shown in a previous pilot study. Hypoxic injury of intra-abdominal organs and/or tissues may cause the release of Danger Associated Molecular Patterns (DAMPs). It is known that after trauma and sepsis, the release of DAMPs is associated with immunoparalysis and a higher susceptibility to infectious complications. The use of low pressure PNP may reduce hypoxic injury and the release of DAMPs and thereby contributing to a better preservation of innate immune function which may help to reduce the risk of infectious complications.

Objective:

Primary objectives:

- To establish the relationship between the use of deep neuromuscular blockade (NMB) with low pressure pneumoperitoneum (PNP) and the quality of recovery after RARP.
- To establish the relationship between the use of deep neuromuscular blockade (NMB) with low pressure pneumoperitoneum (PNP) and innate immune function after RARP.

Secondary objectives:

- To study whether low pressure PNP and/or deep NMB affects the perfusion of the parietal peritoneal layer during RARP.

Study design: A mono-center, randomized controlled clinical trial.

Study population: Adult patients undergoing elective RARP without extended lymph node dissection.

Intervention: The participants will be randomly assigned in a 1:1 fashion to:

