10.2 Secondary study parameter(s)

Study parameters/endpoints	Presentation of data
QOR-40 (primary endpoint), SF-36, McGill pain questionnaire	Quantitative
Pain scores	Quantitative
PONV	Quantitative
Medication use	Quantitative
Length of hospital stay (days)	Quantitative
Time to reach discharge criteria	Quantitative
Surgical conditions	Quantitative
Mesothelial hypoxia (HIF1-alfa mRNA expression)	Quantitative
Histological peritoneal mesothelial cell injury and plasma levels of DAMPs and cytokines	Quantitative
Ex vivo immune function (primary endpoint 2)	Quantitative

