	Definitions	Modes of therapy
I	Any deviation from the normal postoperative course	No pharmacological or surgical treatment, endoscopic or radiological interventions were required. Acceptable therapeutic regimens are drugs such as anti-emetics, antipyretics, analgesics, diuretics and electrolytes and physiotherapy. Wound infections of small abscess requiring incision at bedside is within this category.
II	Normal course altered	Pharmacological management other than in grad 1. Blood transfusions and total parenteral nutrition are also included.
III	Complications that require intervention of various degrees	Sub-classified into: 
 - Grade IIIa – Complications that require an intervention performed under local anesthesia - Grade IIIb – Interventions that require general or epidural anesthesia
IV	Complications threatening life of patients (incl. CNS complication), requiring ICU support	Sub-classified into: 
 - Grade IVa - Single organ dysfunction (incl. dialysis) - Grade IVb – Multi-organ dysfunction
V	Death of a patient	

Table 3: Overview of study endpoints

	QOR-40 (primary endpoint in main study)	Anti-coagulated blood (ex vivo leukocyte responses, DAMP and cytokines)	Indocyanine green fluorescence of parietal peritoneum	Peritoneal tissue biopsy (histology and HIF1alpha mRNA)	Pain scores, PONV, Analgesia use	Complications, Discharge criteria, Length of hospital days	SF-36 QoL	McGill Pain Questionair
-1 day	X	X					X	
After trocar introduction			X	X				
At end of IAP				X				
1hr					X			
8 hr					X			
24 hr	X	X			X	X		
48 hr					X	X		
10-12 days	X	X					X	
3 months						X	X	X

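### The perfusion index is tested as a primary endpoint at 0.05 although its objective is secondary, it has no sample-size basis, and section 10.1 names a different site from the rest of the protocol.

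*Combined protocol and SAP*

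**What the plan says.** **Perfusion as primary.** The synopsis (under primary endpoints) and section 8.1 (main study endpoints) both list "Perfusion index of the parietal peritoneum as calculated from the slope of ICG fluorescence intensity, and time to maximal intensity in seconds". Section 10.1 repeats the item with another site, "Perfusion index in sigmoid as calculated from the slope of ICG fluorescence intensity, and time to maximal intensity in seconds", and specifies a factorial ANCOVA adjusted for age and gender, with significance at 0.05.

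**Perfusion as secondary.** The synopsis and section 2 give two primary objectives, quality of recovery and immune function. Both place this among the secondary objectives: "To study whether low pressure PNP and/or deep NMB affects the perfusion of the parietal peritoneal layer during RARP".

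**Sample size.** Section 4.4 opens with "With this number of patients we will have sufficient power for the primary and secondary analyses" and then gives calculations for QoR-40, IL-6 and IL-10 only.

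**Multiplicity.** The only correction is within the cytokine pair: "As the primary endpoint includes changes in both IL-6 and IL-10 release, Bonferroni correction for multiple comparisons will be used". No text says how the primary results are to be read together.

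**Tags.** The table in section 10.2 has the rows "QOR-40 (primary endpoint), SF-36, McGill pain questionnaire" and "Ex vivo immune function (primary endpoint 2", and no row for perfusion. Table 3 tags one column, "QOR-40 (primary endpoint in main study".

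**The concern.** An endpoint's rank decides what a trial may claim from it. Here three lists give perfusion primary or main rank and two statements of objectives give it secondary rank, so the choice could be made after the results are known. The opportunity is real: the introduction already reports a significantly shorter time to maximum fluorescence at 8 mmHg in the group's earlier colorectal study. A significant perfusion difference could be presented as a positive primary result while quality of recovery and immune function, the two stated primary objectives, both show nothing.

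Two further gaps add room for choice. Section 10.1 names the sigmoid, which does not fit the procedures. It also names the slope and the time to maximum without saying whether they form one test or two.

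**Working it through.** **1. The plan's own sample sizes.** Inputs from section 4.4: 90% power; QoR-40 difference 10, SD 15, alpha 0.05; IL-6 difference 3,000, SD 4,000, alpha 0.025; IL-10 difference 50, SD 65, alpha 0.025. Two-sided testing is my assumption, since the plan does not state it. Normal approximation, per arm: n = 2 × (z for 1 − alpha/2 + z for power)² / (difference/SD)².

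- QoR-40: 2 × (1.960 + 1.282)² / 0.667² = 47.3, so 48.
- IL-6: 2 × (2.241 + 1.282)² / 0.750² = 44.1, so 45.
- IL-10: 2 × (2.241 + 1.282)² / 0.769² = 41.9, so 42.

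All three stated figures reproduce. None concerns perfusion, and the available text gives no target difference or SD for it.

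**2. What 48 per arm can detect for perfusion.** At two-sided 0.05, detectable difference in SD units = (1.960 + z for power) × √(2/48).

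- 80% power: (1.960 + 0.842) × 0.204 = 0.57 SD (0.58 by t-test).
- 90% power: (1.960 + 1.282) × 0.204 = 0.66 SD (0.67 by t-test).

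The second value is close to the trial's QoR-40 design effect, 10/15 = 0.67. The documents do not say whether a perfusion difference of this size is expected.

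**3. Chance of at least one false primary claim.** Alphas from section 10.1: QoR-40 0.05, IL-6 0.025, IL-10 0.025, perfusion 0.05. Conditions: any single success may be claimed, all null hypotheses hold, tests independent.

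- Without perfusion: 1 − 0.95 × 0.975² = 9.7%.
- Perfusion as one test: 1 − 0.95 × 0.975² × 0.95 = 14.2%, an increase of 4.5 points.
- Perfusion as two tests at 0.05 each: 1 − 0.95 × 0.975² × 0.95² = 18.5%, an increase of 8.8 points.

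The documents give no correlations. In simulations with assumed positive values (0 to 0.6 between families, 0.3 to 0.8 between cytokines, 0.5 to 0.9 between the two perfusion measures), the three figures fall to about 8 to 10%, 11 to 14% and 13 to 18%.

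**4. Site.** The synopsis, section 5.1, section 8.1 and Table 3 refer to the peritoneum, in most places explicitly the parietal peritoneum, and section 8.3 aims the camera at the lateral abdominal wall. Only section 10.1 says sigmoid, and no sigmoid recording is described.

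**The case against.** **The plan does label perfusion primary.** The synopsis, section 8.1 and section 10.1 all do so in their headings. This stands. A reader might infer from the bracketed tags that the plan's own labels leave perfusion out. They do not: only the tags in section 10.2 and Table 3 omit it. Those tags are weak evidence of rank. Section 10.2 is headed as secondary parameters and has no perfusion row, which fits perfusion being primary at least as well; Table 3 also leaves the blood and immune column untagged, although immune function is a stated primary objective. The case rests on the objectives and on section 4.4.

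**The introduction lists perfusion first among its aims.** That list ends with clinical outcomes, quality of recovery among them, so its order is not a ranking.

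**The power sentence leads into a two-item list and may cover only those items.** That is the natural reading. Perfusion then still has no calculation, and the sentence needs only a small clarification.

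**The error rates require a rule that the plan does not state, and most of the 14.2% exists without perfusion.** Both points stand. Section 3 also speaks of the perfusion index in the singular, which favours one test over two.

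**The site is not in doubt in practice.** Agreed: sigmoid in section 10.1 is an isolated inconsistency, but it sits in the analysis text.

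**Conclusion.** The contradiction is real and affects what the trial may claim. Perfusion is listed as primary and tested at 0.05 outside the only correction, against two statements that its objective is secondary and with no sample-size basis. The analysis section also names the wrong site relative to the procedures and leaves the number of tests open. It should be resolved before unblinding.

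The size, 9.7% rising to 14.2% or at most 18.5%, is an illustration that holds only under an any-one-success reading, with all null hypotheses true and tests independent.

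Two stronger readings are tempting. One is that the trial's false-positive rate simply is 14.2% or 18.5%; the plan states no such success rule. The other is that the trial is underpowered for perfusion; without an expected difference or SD, neither adequate nor inadequate power can be shown.

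How QoR-40 and the cytokines should share alpha is a judgement outside this point. The conflict between day 7 and days 10-12 for the cytokines is a separate matter.

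**What to change.** Before unblinding:

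1. Move perfusion to the secondary endpoints in the synopsis, section 8.1 and section 10.1, to agree with the stated objectives. Add it to sections 8.2 and 10.2 and carry over the ANCOVA from section 10.1. Section 10.2 says only that data are quantitative, so without this step perfusion would lose its only specified analysis. If perfusion is to stay primary, make the objectives agree and give it a sample-size basis and a stated share of alpha.
2. In section 10.1, replace sigmoid with parietal peritoneum. Name either the slope or the time to maximum as the main perfusion measure, or correct for two.
3. In section 4.4, limit the power sentence to QoR-40, IL-6 and IL-10.

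Cost: moving perfusion changes text only and adds no patients or procedures, but perfusion can then no longer support a primary claim. Keeping it primary with a smaller alpha costs sensitivity. At 0.025, for example, 48 per arm detects 0.64 SD with 80% power or 0.73 SD with 90% (t-test), against 0.58 and 0.67 at 0.05.
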